4.7 Missing Data and Dropouts

All eligible providers may not respond to surveys or to particular survey questions. In order to minimize survey non-response we will administer the survey electronically in a format that will prompt PCPs to answer missed questions. We will also send multiple reminders of the survey and provide PCPs who do not have CDS access an incentive of \$150 to complete baseline and 6-month surveys, and PCPs who do have CDS access an incentive of \$300 to complete baseline and 6-month surveys and submit feedback via the CDS feedback tab.

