1.2 Primary and Secondary Outcomes (Endpoints)

Primary Aims:

- 1) To program an OUD-CDS tool based on a NIDA-Blending Initiative white paper “Clinical Decision Support for Opioid Use Disorders: Working Group Report” and national guidelines (VA (VA 2015), ASAM (ASAM 2015)) for use in an EMR.

Measure 1. Demonstrate that the OUD-CDS is functional and accurate through:

- a) Testing in the EMR test environment,
 - b) Chart audit validation of CDS output, and
 - c) Approval of the tool by specialty addiction physician and PCP pilot testers prior to the full rollout.
- 2) To descriptively analyze PCP acceptability, satisfaction and use rates high enough to demonstrate proof of concept

Measure 2A. By the end of the 6-month pilot intervention, the monthly PCP use rate of the CDS for targeted high-risk patient encounters for PCPs with CDS access will be >60%.

Measure 2B. By the end of the 6-month pilot intervention, >60% of PCPs with CDS access will report feeling confident in assessing and treating OUD

Measure 2C. At the end of the 6-month pilot intervention, >80% of PCPs with CDS access will rate the OUD-CDS ≥ 4 on a 5-point Likert scale of likeliness to recommend use of the tool to their colleagues.

Secondary Aims. We will examine the usefulness of the OUD-CDS tool by comparing pre- and post-intervention rates of screening for OUD in high-risk patients, TAPS use, OUD diagnosis, use of medication-assisted therapy, as well as treatment referral patterns, for 3 groups of PCPs: (1) those with CDS access and buprenorphine certification, (2) PCPs with CDS access but without buprenorphine certification, and (3) PCPs without CDS access.

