3.0 RANDOMIZATION AND FACTORS FOR STRATIFICATION

PCPs who are recruited and are buprenorphine-certified will be placed into the group of PCPs who have OUD-CDS access. PCPs who are recruited and do not have buprenorphine certification will be randomized to receive or not receive access to the OUD-CDS. We will be aware of practice location, patient panel size and number of patients for whom the CDS-OUD was triggered and can analyze results based on individual practice location or panel, but given the small nature of this pilot project we do not anticipate statistically meaningful information from these factors.

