4.2 Statistical Methods for Primary and Secondary Outcomes

This pilot study for OUD-CDS feasibility and usability will not have a statistical endpoint. Provider characteristics, patient characteristics, and OUD-CDS use rates will be tracked and described. Pre- and post-intervention surveys of provider confidence in OUD assessment and treatment as well as satisfaction and usability of the OUD-CDS will be described.

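### Does the missing-data section need a rule for how PCPs who give no survey answer count in Measures 2B and 2C?

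*SAP*

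**What the plan says.** Section 1.2 gives the second primary aim three numeric targets. Two depend on PCPs' own answers. Measure 2B asks that more than 60% "of PCPs with CDS access will report feeling confident in assessing and treating OUD". Measure 2C reads "At the end of the 6-month pilot intervention, >80% of PCPs with CDS access will rate the OUD-CDS" at 4 or higher on a five-point scale. In both, the base of the percentage is the group given the tool.

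Section 4.7, headed for missing data and dropouts, expects gaps: "All eligible providers may not respond to surveys or to particular survey questions". Its response is preventive: "In order to minimize survey non-response we will administer the survey electronically", with prompts for skipped items, repeated reminders, and payments of $150 without access or $300 with access. The larger payment is "to complete baseline and 6-month surveys and submit feedback via the CDS feedback tab". Nothing is said about answers that stay missing, and dropouts appear only in the heading.

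Section 4.2 states that there is no statistical endpoint and that the survey results, "as well as satisfaction and usability of the OUD-CDS will be described". Section 4.3 rules out testing and power calculations.

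**The concern.** A section on missing data that covers only prevention looks unfinished, and here it touches two primary measures. The aim speaks of "use rates high enough to demonstrate proof of concept", and 2B and 2C are fixed cut-offs in support of it. If the analyst divided by responders instead of by everyone with access, the percentage would rise, and with a few dozen PCPs one or two answers can move it across the line. A report giving only the more favourable figure would then show a target as met when the stated base does not support it. The same question arises for a returned survey with the key item blank and for a PCP who leaves before month 6.

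**Working it through.** The plan states no figure for this point, so there is none to reproduce. Two questions matter: how far apart the two percentages can be, and which of them the plan calls for.

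**Inputs from the SAP.** Targets of >60% (2B) and >80% (2C), Section 1.2. Total PCPs 37–43, Sections 4.1.1 and 4.1.2. All certified PCPs get access and non-certified PCPs are randomized, Section 3.0.

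**Assumptions, not in the SAP.** A 1:1 split of non-certified PCPs, at least one PCP in each of the three groups in Section 1.2, and the non-response rate.

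**Number with access.** With *N* PCPs in total and *c* certified, n = c + (N − c)/2.
- N = 37, c = 1: 1 + 18 = 19
- N = 42, c = 14: 14 + 14 = 28
- N = 43, c = 41: 41 + 1 = 42

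**Distance between the two percentages.** With *x* favourable answers and *m* missing, x/(n − m) − x/n = [x/(n − m)] × (m/n). The gap is the responders' percentage times the fraction missing.

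For n = 28 and m = 3:

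| Measure | Responders only | All with access | Gap | Range over the unseen answers |
|---|---|---|---|---|
| 2C, x = 22 | 22/25 = 88.0% | 22/28 = 78.6% | 88.0 × 3/28 = 9.4 points | 22/28 to 25/28 = 78.6–89.3% |
| 2B, x = 16 | 16/25 = 64.0% | 16/28 = 57.1% | 64.0 × 3/28 = 6.9 points | 16/28 to 19/28 = 57.1–67.9% |

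**When they disagree about the target.** This needs x/(n − m) > t and x/n ≤ t. For n = 28, m = 3, that is x = 21 or 22 for 2C and x = 16 alone for 2B. Taking X as binomial among the 25 responders:

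| Responders' true rate above target | 2C | 2B |
|---|---|---|
| 5 points | 0.428 | 0.163 |
| 10 points | 0.365 | 0.134 |
| 15 points | 0.120 | 0.078 |

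Over n = 19–42 with 10% missing (m rounded half up), the chance of disagreement is:
- 5 points above: 2C 24–69%, 2B 15–43%
- 10 points above: 2C 18–60%, 2B 11–35%
- 15 points above: 2C 4–30%, 2B 6–23%

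With 5% missing and a rate 5 points above, the ranges are 0–39% and 0–29%. Some group sizes cannot disagree at all. For n = 21, m = 1 on 2C, exceeding 80% of 20 needs x ≥ 17, while staying at or below 80% of 21 needs x ≤ 16.

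**Which percentage the plan calls for.** Set Section 1.2 beside Section 4.7. The first fixes the base as PCPs with access. The second says some of them may not answer but does not redefine the base. A PCP who has not reported confidence, or has not rated the tool, is still one of those with access and is not among those who reported or rated. The result is x/n. Section 4.2 says the surveys will be described, which does not override the base fixed in Section 1.2.

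**The case for a change.** The strongest case for a change is that a fixed threshold needs a fixed denominator, and that handling of missing answers belongs in a SAP, above all in a section with that heading. Describing survey results commonly means percentages of those who answered, so an analyst might slip into that without noticing. Even a literal reading leaves open whether a PCP who leaves before month 6 still counts as having access. If non-responders count as not meeting the measure, 20% non-response puts 2C out of reach: with 25 having access and 20 answering, 21 favourable ratings are needed.

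Part of this stands. No sentence confirms the treatment of leavers or blank items, and the arithmetic is right. But a responders-only percentage would replace a base that Section 1.2 states, so it would be a departure from the plan and not a choice left open by it. That 2C is hard to meet when many do not answer follows from the stated target.

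It could also be argued that infrequent users would be the ones not to answer, since the payment covers both surveys and tool feedback, and Section 3.0 says the team will know the "number of patients for whom the CDS-OUD was triggered". Neither fact shows who will fail to answer. The access group is offered twice the payment of the other group, which could equally favour high response. The direction of any bias is conjecture.

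**Conclusion.** No change is needed. Section 4.7 lacks detail, but the plan followed as written gives the all-with-access percentage for 2B and 2C, which can never exceed the responders-only one. The difference equals the responders' percentage times the fraction missing: 9.4 points for 2C and 6.9 for 2B in the example, and little if response is nearly complete. Those sizes rest on an access count, a 1:1 split and non-response rates that the SAP does not give, and the worked counts were picked because they straddle the targets.

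The consequence is also limited. There is no test or statistical endpoint, Measure 2A is a rate over encounters and does not depend on survey response, and with 19–42 PCPs ordinary reporting of counts shows both percentages. A sentence confirming that leavers and blank items stay in the denominator would do no harm, but it would mainly restate the base that Section 1.2 already fixes.

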4.8 Demographic and Baseline Characteristics

Baseline demographic and practice variables (e.g., years in practice, size of patient panel, etc.) will be summarized for PCPs enrolled in this study.

4.9 Safety Analysis

In this pilot study, we are not trying to change the standard of care for OUD treatment in primary care, but rather helping PCPs achieve this standard of care in OUD treatment. PCPs are trained that, as with other CDS tools, the OUD-CDS is meant to supplement but not supersede clinical judgment. PCPs can choose to follow or not follow the guidance of the CDS at any given time for any given patient encounter, and PCPs are trained to let the research team know via the Feedback tab in the CDS when their clinical judgment is inconsistent with the CDS recommendations. This feedback will be monitored by the treatment team and the CDS algorithms adjusted if indicated.

An independent CTN DSMB will monitor this study. The DSMB will communicate regarding what type of reports will be needed, as well as frequency.
